8.5 Exploratory Analysis

Exploratory efficacy analyses will be presented in Statistical Documentation.

Treatment-by-center interaction will be assessed at Day 42 by including the treatment-by-center-by-visit interaction in the model. Results for study centers will be displayed from largest center to smallest center.

SAP 405-201-00013

Line Item score will be performed for AISRS and ASRS on Change from baseline of the double-blind treatment period to Day 42 using the MMRM model for AISRS and ASRS, where Cohen's D Effect Size¹⁰ is the difference between the two means divided by their standard deviation [as defined by Cohen's D and reviewed on pages 4-6 from the Sage book "Effect Size for ANOVA Designs" (Vol 129) by Cortina and Nouri]. For MMRM (using SAS PROC MIXED), or ANCOVA (Using SAS PROC GLM), LSMean difference of treatment effects for the between centanafadine and placebo groups, and the standard error of the difference (Stderr) will be obtained with an Estimate statement. Let n_1 and n_2 denote the respective sample sizes of the two groups to compare, Effect Size = $d = (\text{LSMean}_1 - \text{LSMean}_2) / \sigma$, where $\sigma = \frac{\text{Stderr}}{\sqrt{\frac{1}{n_1} + \frac{1}{n_2}}}$.

9 Safety Analysis

Standard safety variables to be analyzed include AEs, clinical laboratory tests, vital signs, electrocardiograms (ECGs), body weight, waist circumference, and BMI. In addition, data from the following safety scales will be evaluated: C-SSRS and Study Medication Withdrawal Questionnaire (SMWQ).

Analyses of the double-blind treatment period safety data will be performed on the Safety Sample unless indicated otherwise.

The Safety Sample will also be analyzed for the single-blind placebo lead-in period safety data, as applicable, by treatment groups the subjects eventually being assigned in the double-blind treatment period.

9.1 Adverse Events

All adverse events (AEs) will be coded by system organ class (SOC) and Medical Dictionary for Regulatory Activities (MedDRA) Preferred Term (PT). The incidence of the following events will be summarized:

- a) Treatment-emergent AEs (TEAEs)
- b) TEAEs by severity
- c) TEAEs potentially causally related to the IMP
- d) TEAEs with an outcome of death
- e) Serious TEAEs
- f) TEAEs leading to discontinuation of the IMP

SAP 405-201-00013

- g) Treatment-emergent Adverse Events of Special Interest (AESI)
- h) Abuse-related TEAEs and TEAEs involving MHIs (Medication handling irregularities)

AEs will be classified by Primary SOC and PT according to the MedDRA. AEs that are gender-specific, e.g., ovarian cancer, will have their incidence rates evaluated for the specific gender.

Incidence of TEAEs will be summarized by double-blind treatment group for the double-blind treatment period. Incidence of TEAEs by SOC and MedDRA PT will be summarized for sex and race.

Adverse Events of Special Interest

Newly acquired skin eruptions that are non-traumatic will be considered AESIs. These may include but are not limited to eruptions such as skin rashes, skin irritations, skin reactions, or acneiform lesions. This does not include localized contact irritation at ECG lead sites due to application or removal of lead adhesive.

Refer to the separate rash workup plan for complete details, including reporting forms, and extra measures that must be performed to characterize any skin AESI of a newly acquired skin eruption that is non-traumatic. The trial site will have a local designated dermatologist available for immediate consultation during the trial for these AESIs.

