3.1 Type/Design of Trial

This trial is a phase 3, randomized, double-blind, multicenter, placebo-controlled, parallel-group trial to confirm the efficacy, safety, and tolerability of centanafadine SR (200 mg TDD or 400 mg TDD) compared to placebo for the treatment of adults with ADHD. The trial population will include male and female subjects 18 to 55 years of age (inclusive) with a current diagnosis of ADHD as confirmed by the Adult ADHD Clinical Diagnostic Scale (ACDS) Version 1.2 at screening.

The trial will have 4 periods: (1) screening and washout; (2) 1 week single-blind placebo run-in; (3) 6-week double blind treatment; and (4) 7-day follow-up period (follow-up telephone calls at 1, 3, and 5 days after the last dose of IMP, and in-clinic visits 2 and 7 days after the last dose of IMP) for subjects who complete the trial, and decide to enroll in Trial 405-201-00015. For subjects who terminate early, decide to not enroll in Trial 405-201-00015, or who are not eligible to enroll in Trial 405-201-00015, they will be required to participate in the 7-day follow-up period as well as participate in an additional follow-up telephone call 10 days after the last dose of IMP. Subjects randomized to receive a TDD of 200 mg centanafadine SR will start at their target dose at the start of the double-blind treatment period. Subjects randomized to receive a TDD of 400 mg centanafadine SR will start the double-blind treatment period at the TDD of 200 mg centanafadine SR for 7 days, before they are escalated to their target TDD of 400 mg for a total of approximately 42 days of treatment. Subjects will be required to visit the site up to 12 times over the trial. See [Figure 3.1-1](#) for a schematic of the trial design.

Protocol 405-201-00013

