3.7.1.5 Visits 10 Through 14 (Follow-up)

All subjects, whether they complete the trial or are withdrawn prematurely for any reason, will be followed up for a safety evaluation for 7 days (follow-up telephone calls at 1, 3, and 5 days after the last dose of IMP, and in-clinic visits 2 and 7 days after the last dose of IMP). The assessments described in the Follow-up Schedule of Assessments (Table 3.7-2) will be completed. The following should also be noted:

Subjects who complete both the 6-week double-blind treatment period, the 7-day follow-up period (follow-up telephone calls at 1, 3, and 5 days after the last dose of IMP, and in-clinic visits 2 and 7 days after the last dose of IMP), and who refrain from using prohibited medications (Section 4.1) after the IMP is stopped, may be eligible to enroll into Trial 405-201-00015, which is a 12-month, observational, open-label trial to evaluate the long-term safety and tolerability of subjects with ADHD who previously participated in Trials 405-201-00013 or 405-201-00014. For subjects who early terminate or decline participation in the open-label trial, they will be instructed to refrain from utilizing prohibited concomitant medications (Section 4.1), including ADHD treatments, until after the follow-up telephone call 10 days after the last dose of IMP (Section 3.7.1.6). Subjects who will be rolling over into the open-label trial will need to sign the Trial 405-201-00015 informed consent form prior to activities performed at the 7-day follow-up visit of Trial 405-201-00013.

Protocol 405-201-00013

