This amendment serves to provide clarifications, additions, and subtractions to trial procedures intended to gather additional safety data during the follow-up period. In addition, administrative clarifications were made, including corrections to typographical, punctuation, and formatting errors. These changes were minor and do not change the design or content of the protocol, and therefore, are not summarized in this appendix.

BACKGROUND:

These changes to clinical trial protocol 405-201-00013, issued 08 Mar 2018, were made to address preliminary FDA comments received on 27 Apr 2018 in regards to the Type C briefing package, and to address other minor administrative changes.

MODIFICATIONS TO PROTOCOL:**General Revisions:**

- Added additional follow-up contacts to be conducted via telephone on 1, 3, and 5 days after the last dose of IMP for all subjects enrolled in Trial 405-201-00013.
- Revised the last day of subject contact from Day +14 to Day +10 for subjects that do not complete Trial 405-201-00013, are not eligible for, or do not rollover to Trial 405-201-00015.
- Added criteria excluding subjects with HIV seropositive status/acquired immunodeficiency syndrome, seropositive status for hepatitis B (ie, HBsAg positive), or hepatitis C (ie, anti-HCV positive and HCV RNA positive).
- Clarified that pregnancy testing at screening should only be performed on FOCBP.
- Added wording in the clinical laboratory table indicating that a CPK reflex for isoenzymes if $CPK > 3 \times ULN$; serum and urine myoglobin collected if $CPK > 5 \times ULN$, and that the urine drug screen should include methylphenidate (ritalinic acid).
- Revised exclusion language regarding participating in other prior clinical trials.
- Added statistical language to address new requirements set forth by the ICH E9(R1) Addendum.
- Removed Appendices 5-8 from the protocol and replaced in-text references to these appendices with reference to external documentation.
- Revised postmenopausal criteria to be aligned with template text.

Protocol 405-201-00013

- Clarified that SMWQ will be completed by the subject at the site and completed remotely for non-site visits.
- Removed CYP2D6 inhibitors and substrates from the List of Medications Prohibited Before the Trial table and the List of Medications Prohibited During the Trial table.
- Corrected various typographical errors and provided clarifications to text.

ADDITIONAL RISK TO THE SUBJECT:

There is no additional risk to the subjects.

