9.1.1 Adverse Events in the Double-Blind Treatment Period

TEAEs in the double-blind treatment period are defined as AEs with an onset date on or after the start of double-blind treatment. In more detail, TEAEs are all adverse events which started after start of double-blind IMP; or if the event was continuous from end of the single-blind placebo run-in period and was worsening, serious, study drug related, or resulted in death, discontinuation, interruption or reduction of study therapy. Adverse Events occurring up to 30 days after the last day of double-blind dosing will be included in the summary tables.

The incidence of AEs in the double-blind treatment period will be tabulated by treatment group and overall using the Safety Sample. Incidence of TEAE during the double-blind treatment period of at least 5% in either centanafadine group and also greater than placebo by SOC and MedDRA PT will be provided.

Unless otherwise specified, in general, analysis of safety data will be performed on observed case and for last visit.

SAP 405-201-00013

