- CT-6.2.1 Summary of Mean Change from Baseline of the Double-Blind Treatment Period to the Double-Blind Treatment Period by Study Day in Adult ADHD Investigator Symptom Rating Scale (AISRS) Total Score in the Subgroup of Whites - MMRM (Efficacy Sample)
- CT-6.2.2 Summary of Mean Change from Baseline of the Double-Blind Treatment Period to the Double-Blind Treatment Period by Study Day in Adult ADHD Investigator Symptom Rating Scale (AISRS) Total Score in the Subgroup of All Other Races - MMRM (Efficacy Sample)
- CT-7.1 Extent of Exposure to Study Medication During the Double-Blind Treatment Period (Safety Sample)
- CT-7.2 Number and Percentage of Subjects Receiving Study Medication and Mean and Range of Average Daily Dose in the Double-Blind Treatment Period (Safety Sample)
- CT-8.1.1 Adverse Events During the Double-Blind Treatment Period (All Causalities) (Safety Sample)
- CT-8.1.2 Adverse Events During the Single-Blind Placebo Run-in Period (All Causalities) (Safety Sample)
- CT-8.2.1.1 Incidence of TEAEs During the Double-Blind Treatment Period by System Organ Class and MedDRA Preferred Term (Safety Sample)
- CT-8.2.1.2 Incidence of TEAEs During the Double-Blind Treatment Period by System Organ Class, MedDRA Preferred Term and Severity (Safety Sample)

SAP 405-201-00013

- CT-8.2.1.3 Incidence of TEAE During the Double-Blind Treatment Period of at Least 5% in Any Centanafadine Group and Greater Than Placebo by System Organ Class and MedDRA Preferred Term (Safety Sample)
- CT-8.2.1.4 Incidence of TEAEs During the Double-Blind Treatment Period by System Organ Class and MedDRA Preferred Term, by Sex (Safety Sample)
- CT-8.2.1.5 Incidence of TEAEs During the Double-Blind Treatment Period by System Organ Class and MedDRA Preferred Term, by Race (Safety Sample)
- CT-8.2.1.6 Incidence of Non-Serious TEAEs During the Double-Blind Treatment Period of at Least 5% in Any Centanafadine Group and Greater Than Placebo by System Organ Class and MedDRA Preferred Term (Safety Sample)
- CT-8.2.1.7 Incidence of TEAE During the Double-Blind Treatment Period of at Least 2% in Any Centanafadine Group and Greater Than Placebo by System Organ Class and MedDRA Preferred Term (Safety Sample)
- CT-8.2.1.8 Incidence and Occurrence (Number of Events) of Serious TEAEs by System Organ Class and MedDRA Preferred Term (Safety Sample)

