- CT-8.2.1.9 Incidence and Occurrence (Number of Events) of Potentially Drug-Related Serious TEAEs by System Organ Class and MedDRA Preferred Term (Safety Sample)
- CT-8.2.1.10 Incidence and Occurrence (Number of Events) of Non-Serious TEAEs by System Organ Class and MedDRA Preferred Term (Safety Sample)
- CT-8.2.2 Incidence of AEs During the Single-Blind Placebo Run-in Period by System Organ Class and MedDRA Preferred Term (Safety Sample)
- CT-8.3.1 Incidence of Potentially Drug-Related TEAEs During the Double-Blind Treatment Period by System Organ Class and MedDRA Preferred Term (Safety Sample)
- CT-8.3.2 Incidence of Potentially Drug-Related TEAEs During the Double-Blind Treatment Period by System Organ Class, MedDRA Preferred Term and Severity (Safety Sample)
- CT-8.4.1.1 Incidence of Deaths Due to TEAEs During the Double-Blind Treatment Period by System Organ Class and MedDRA Preferred Term (Safety Sample)
- CT-8.4.1.2 Incidence of Deaths Due to TEAEs During the Double-Blind Treatment Period by System Organ Class and MedDRA Preferred Term and Severity (Safety Sample)
- CT-8.4.2 Incidence of Deaths Due to AEs During the Single-Blind Placebo Run-in Period by System Organ Class and MedDRA Preferred Term (Safety Sample)
- CT-8.5.1.1 Incidence of Serious TEAEs During the Double-Blind Treatment Period by System Organ Class and MedDRA Preferred Term (Safety Sample)
- CT-8.5.1.2 Incidence of Serious TEAEs During the Double-Blind Treatment Period by System Organ Class, MedDRA Preferred Term and Severity (Safety Sample)
- CT-8.5.2.1 Incidence of Serious AEs During the Single-Blind Placebo Run-in Period by System Organ Class and MedDRA Preferred Term (Safety Sample)
- CT-8.6.1 Incidence of TEAEs Resulting in Discontinuation of Study Medication During the Double-Blind Treatment Period by System Organ Class and MedDRA Preferred Term (Safety Sample)
- CT-8.6.2 Incidence of TEAEs Resulting in Discontinuation of Study Medication During the Double-Blind Treatment Period by System Organ Class, MedDRA Preferred Term and Severity (Safety Sample)
- CT-8.7.1 Incidence of Treatment-Emergent Adverse Events of Special Interests (AESIs) During the Double-Blind Treatment Period by System Organ Class and MedDRA Preferred Term (Safety Sample)
- CT-8.7.2 Incidence of Treatment-Emergent Adverse Events of Special Interests (AESIs) During the Double-Blind Treatment Period by System Organ Class and MedDRA Preferred Term and Severity (Safety Sample)

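### The TEAE tables pool events starting on drug with events starting up to 30 days after the last dose, and no follow-up AE table is planned to separate them

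*SAP*

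**What the plan says.** SAP 9.1.1 fixes the start of the TEAE window by treatment: "TEAEs in the double-blind treatment period are defined as AEs with an onset date on or after the start of double-blind treatment". The end of the window comes from a counting rule in the same section: "Adverse Events occurring up to 30 days after the last day of double-blind dosing will be included in the summary tables". SAP 9.1 gives the breakdown, by arm and for one period: "Incidence of TEAEs will be summarized by double-blind treatment group for the double-blind treatment period".

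The list in SAP section 13 follows this. CT-8.2.1.1 is titled "Incidence of TEAEs During the Double-Blind Treatment Period by System Organ Class and MedDRA Preferred Term (Safety Sample" and CT-8.2.2 "Incidence of AEs During the Single-Blind Placebo Run-in Period by System Organ Class and MedDRA Preferred Term (Safety Sample" (closing brackets omitted). Most of the CT-8 TEAE tables carry the double-blind label, and the run-in is the only other AE period tabulated. The ESAM tables, CT-17.1 to CT-17.4, use the same two periods.

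On collection, Protocol 3.7.1.5 says that all subjects "will be followed up for a safety evaluation for 7 days", with calls at 1, 3 and 5 days and visits at 2 and 7 days. Section 3.7.1.6 adds a day-10 call for subjects who do not enter the open-label trial. Table 3.7-2 marks adverse events at every one of these contacts. Protocol Appendix 5 shows that Amendment 1 added the day 1, 3 and 5 calls as part of changes to "trial procedures intended to gather additional safety data during the follow-up period".

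**The concern.** The trial collects adverse events after dosing stops, and withdrawal is a named safety question (Protocol 3.5.4, SMWQ; Protocol 5.5, abuse-potential monitoring). But the AE tables give these events no place of their own. If fatigue, low mood or sleep disturbance appears when centanafadine is stopped, the subject is counted in the same row as one who had that term during dosing, under a double-blind-period label.

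Two things are at stake. A cluster of post-dose events by preferred term would not stand out in any planned incidence table. And the table of TEAEs reaching 5% on a centanafadine arm and exceeding placebo (SAP 9.1.1, CT-8.2.1.3) draws on the pooled rows, so a term could enter it through post-dose onsets with nothing to tell the reader so.

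**Working it through.** The plan states no figure on this point, so there is none to reproduce. The check has three parts.

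**1. What is tabulated for follow-up**

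| Data | Collected after last dose | Shown separately for follow-up |
|---|---|---|
| AISRS | days 2 and 7 | yes, CT-5.2.8, CT-5.3.5, CT-5.3.10 |
| SMWQ | days 1, 2, 3, 5, 7, 10 | yes, by study day, CT-15 |
| Concomitant medications | every contact | yes, CT-4.3 |
| Adverse events | every contact | no |

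SAP 10.1 also removes follow-up evaluations, and those more than three days after the last dose, from the double-blind analysis of the scales it names. Adverse events are treated differently, and no reason is given.

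**2. How much of the observation behind a double-blind row is off drug**

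Inputs: dosing "for a total of approximately 42 days of treatment" (Protocol 3.1); a 30-day counting window (SAP 9.1.1); last scheduled AE contact at day 7 or day 10 (Protocol Table 3.7-2, each with a +2-day window). Off-drug share = post-dose days / (42 + post-dose days).

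- Nominal window: 30/72 = 41.7%.
- Contact to day 7: 7/49 = 14.3%; with the +2-day window, 9/51 = 17.6%.
- Contact to day 10: 10/52 = 19.2%; with the +2-day window, 12/54 = 22.2%.

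The share is larger for early stoppers. A subject whose last dose is on Day 14 and who is followed to day 10 has 10/24 = 41.7% of the scheduled observation off drug.

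**3. What a pooled row could hide (assumed rates)**

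The documents give no AE rates by onset, so these are assumptions shown over a range. Let *a* be the on-drug incidence of a term, equal in all arms, and *w* the incidence of post-dose onset on centanafadine, taken as independent of *a* and as zero on placebo.

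Pooled row on centanafadine = 1 − (1 − a)(1 − w). Share of that row with post-dose onset only = 1 − a / pooled.

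| a | w | Pooled, centanafadine | Placebo | Post-dose only |
|---|---|---|---|---|
| 5% | 3% | 1 − 0.95 × 0.97 = 7.85% | 5% | 36.3% |
| 5% | 5% | 1 − 0.95 × 0.95 = 9.75% | 5% | 48.7% |
| 10% | 5% | 1 − 0.90 × 0.95 = 14.5% | 10% | 31.0% |
| 2% | 5% | 1 − 0.98 × 0.95 = 6.9% | 2% | 71.0% |

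In the last line the term passes the 5% rule although its on-drug incidence is 2% in every arm. Passing depends on the rates assumed. With a = 3%, w = 4% gives 1 − 0.97 × 0.96 = 6.9%, which passes, while w = 2% gives 1 − 0.97 × 0.98 = 4.9%, which does not.

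**The case against.** The strongest reply is that withdrawal has its own instrument and analysis. The SMWQ is completed at Day 35, at Day 42/ET and at every follow-up contact (SAP 10.3.6). SAP 9.7 and CT-15 summarize it by arm and study day through follow-up. A reader might infer from the AE tables that withdrawal effects cannot be seen at all; the documents do not support that. What stands is narrower. SAP 9.7 gives descriptive statistics of a total score. A few subjects with one distinct symptom hardly move a mean, and no term, severity or seriousness is shown.

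A reader might also infer that post-dose events will be reported as reactions to treatment. That does not follow either. The CT-8.2 tables are all-causality, and potentially drug-related events have their own tables (CT-8.3.1, CT-8.3.2). The fault is the period label and the missing split.

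Subject-level detail is planned for deaths, serious events, discontinuations, AESIs and abuse-related events (CT-8.7.3, CT-8.8.3, CT-9.1 to CT-9.4), and Protocol 5.5 requires narratives for abuse-related events. That covers the gravest cases. The list contains no listing for ordinary non-serious events, which is where most withdrawal symptoms would be expected to fall.

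It is tempting to express the cost as lost statistical signal. The documents do not support a figure. Any such calculation needs assumed rates, and with a post-dose rate of, say, 0.5% on placebo and 144 subjects (the placebo count in the efficacy output appended to the SAP) fewer than one event is expected (0.005 × 144 = 0.72). The SAP plans no test of AE incidence, so no planned inference is weakened.

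Finally, the SAP states its 30-day rule openly, and section 13 is only a proposed list. Both are true. Neither supplies the split.

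**Conclusion.** The point holds as a reporting gap. SAP 9.1.1 pools on-drug and post-dose onsets under a double-blind label, and no follow-up AE table is planned. Events that emerge on stopping therefore cannot be told from on-drug events in the incidence tables. This rests on the text and the table list alone.

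For a subject dosed 42 days, 14% to 19% of the scheduled AE observation behind those rows is off drug (18% to 22% with the contact windows, 42% nominally). The number of events affected cannot be known from the documents; the 31% to 71% shares above rest on assumed rates, no on-drug difference between arms and no post-dose onsets on placebo.

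The gap does not touch the primary or key secondary analysis, the sample size or alpha. It is a cheap improvement to make, and would let the trial show withdrawal events by preferred term.

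**What to change.** Keep the pooled TEAE tables, and make three additions to SAP 9.1.1 and section 13.

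1. Derive an onset flag: on or before the date of the last double-blind dose, or after it. Add no grace day. The first follow-up call is one day after the last dose, so an extra day would class next-day withdrawal onsets as on-drug.
2. Add a table by arm of AEs with onset after the last dose through the end of the follow-up contacts, by system organ class and preferred term, for all, serious and abuse-related events.
3. Footnote the table of TEAEs at 5% or more and above placebo with the number of subjects per arm whose only onset was after the last dose, or show it with and without them. There is no need to restrict it to on-drug onsets; that would drop delayed drug effects.

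The cost is one derived variable and one or two extra tables. The 30-day rule already needs the onset and last-dose dates, and SAP 6.2 already says which date to use for subjects lost to follow-up. With dates and no times, an event starting later on the day of the last dose still counts as on-drug. Trial conduct does not change.
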